This prospective, open-label, single-arm, single-center clinical study at the University of California, San Diego Department of Dermatology is designed primarily to investigate the safety and efficacy of deoxycholic acid injection for the treatment of upper inner thigh fat. The secondary objective of this study is evaluation of patient-reported satisfaction outcomes after treatment of upper inner thigh fat with deoxycholic acid injection.

III. Subject Selection

A. Inclusion/Exclusion criteria

Inclusion

- 1. Adults aged 18 to 65
- 2. Discrete area of mild-to-moderate excess upper inner thigh fat, amenable to treatment at the discretion of the investigator
- 3. Subjects who score 0 (extremely dissatisfied) to 2 (slightly dissatisfied) on a Subject Self-Rating Scale, pertaining to upper inner thigh fat, with the scale ranging from 0 (extremely dissatisfied) to 6 (extremely satisfied)
- 4. Body mass index (BMI) less than 30 kg/m²
- 5. Stable body weight for previous 6 months (weight within 10 pounds of baseline)
- 6. Subjects must be in stable health, as confirmed by medical history, per investigator judgment
- 7. Subjects must be able to read, sign, and understand the informed consent
- 8. Subjects must we willing to avoid any other treatments to the inner thigh, including cryolipolysis and liposuction, during the study period.
- 9. Subjects must be willing to avoid changes in diet or exercise, any weight loss program, and any weight loss supplements, during the study period.
- 10. Subjects must be able and willing to avoid anticoagulation (aspirin, warfarin, hepain, rivaroxaban) for 1 week prior to each study treatment

Exclusion:

1. History of treatment for inner thigh fat, including cryolipolysis, noninvasive body contouring or liposuction in the last year

- 2. Previous trauma or surgery to pelvis or thighs
- 3. Subjects with an unstable medical condition, as deemed by the investigator
- 4. Women who are pregnant or lactating or plan to become pregnant during the study period
- 5. Lymphedema or edema of thigh
- 6. Excessive skin laxity in the treatment area, as judged by the investigator
- 7. Severe thigh cellulite
- 8. Subjects with any disease in the treatment area, such as dermatologic disease, that may be exacerbated by the study treatment
- 9. Subjects with any condition that may impair the evaluation of inner thigh fat
- 10. Subjects with known bleeding diathesis

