There will be no randomization. Study participants will be treated with deoxycholic acid (Kybella) 10 mg/ mL injected subcutaneously, targeting the medial thigh deep fat compartment (pre-fascial). Subjects will receive deoxycholic acid 2 mg/ cm², with injections of 0.2 mL spaced evenly 1 cm apart within the treatment area. Bilateral upper inner thighs will be treated. Each treatment will consist of a maximum of 8 mL (40 injection sites) of the study drug, with a maximum of 4 mL (20 injection sites) of the study drug for each thigh. All treatments will be performed by a study physician. Subjects will receive 1 to 4 treatment sessions, each spaced 6 weeks +/- 1 week. Treatment #2, #3, or #4 will be pursued if patient desires more treatment, and if there is sufficient fat for treatment, per investigator's judgment.

V. Study Procedures

a) Study visits and parameters to be measured
 All visits in this study will be performed at the UCSD Dermatology Clinic, 3rd floor,
 [name].

Screening/Baseline Visit (Visit 1, Day -14 to 1)

This visit is expected to take approximately 1 hour. The following describes the procedures performed at this visit.

Prior to any screening assessments, informed consent will be obtained by the
investigator. When the subject fully understands the nature of the study and its risks,
the subject will be asked to sign and date the informed consent form. The
investigator will then sign and date the form.

- 2. A detailed medical history of information pertaining to treatment will be obtained.
- 3. The investigator will perform a relevant physical examination.
- 4. Patient's weight will be obtained.
- 5. The subject will be asked to complete the Subject Self-Rating Scale (0 to 6 scale).
- 6. If the subject meets the criteria for the study, the subject will be assigned the next consecutive subject number.
- 7. Females of childbearing age will undergo a urine pregnancy test
- 8. The investigator will determine the patient's eligibility for the study.

First treatment (Visit 2, Day 1)

The treatment visit is expected to take approximately 1 hour. The first treatment may be combined with Screening/ Baseline.

Prior to Kybella treatment:

- 1. Patient will be asked to complete the Subject Self-Rating Scale, rated from 0 to 6.
- 2. Patient's weight will be obtained.
- 3. Concomitant medications and procedures will be confirmed and recorded.
- 4. The investigator will perform a relevant physical examination.

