- 5. Thigh circumference measurement will be obtained with anthropometric tape measure.
 - Thigh circumference will be measured at site of maximum bulge at Screening.
 Vertical distance of this site from the floor will be measured, such that thigh circumference measurements at all following study assessments are performed at the same site.
- 6. Caliper measurement of inner thigh skin-fold thickness will be obtained.

Caliper measurement will be performed at site of maximum bulge at Screening.
 Vertical distance of this site from the floor will be measured, such that caliper measurements at all following study assessments are performed at the same site.

- 7. Thigh gap measurement will be obtained.
 - Patient will be asked to stand with legs at a fixed distance apart. Measurement
 will be performed between sites of maximum bulge at Screening. Vertical
 distance of these sites from the floor will be measured, such that thigh gap
 measurements at all following study assessments are performed at the same sites.
- 8. Pre-treatment photographs will be taken.
 - Patients will be asked to stand with feet apart at a uniform distance.

 Anteroposterior and posteroanterior photos will be taken.

Treatment:

9. Deoxycholic acid (Kybella) 10 mg/ mL will be injected subcutaneously, targeting the medial thigh deep fat compartment (pre-fascial). Subjects will receive deoxycholic acid 2 mg/ cm2, with injections of 0.2 mL spaced evenly 1 cm apart within the treatment area. Bilateral thighs will be treated. Each treatment will consist of a maximum of 8 mL (40 injection sites) of the study drug, with a maximum of 4 mL (20 injection sites) of the study drug for each thigh. All treatments will be performed by a study physician.

Post-Treatment Phone Call #1 (Day 3)

Phone call expected to take 5-10 minutes.

1. Two days after treatment, patient will be called and asked to report adverse events since last treatment. All adverse events will be recorded.

Second treatment (+/-) (Day 36 to 50)

The treatment visit is expected to take approximately 1 hour.

Prior to Kybella treatment:

1. Patient will be asked to complete the Subject Self-Rating Scale, rated from 0 to 6.

- 2. Patient's weight will be obtained.
- 3. Concomitant medications and procedures will be confirmed and recorded.
- 4. Adverse events will be recorded.
- 5. The investigator will perform a relevant physical examination.
- 6. Thigh circumference measurement will be obtained with anthropometric tape measure.

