 Vertical distance of this site from the floor will be measured, such that thigh circumference measurements at all following study assessments are performed at the same site.
- 8. Caliper measurement of inner thigh skin-fold thickness will be obtained.
 - Caliper measurement will be performed at site of maximum bulge at Screening.
 Vertical distance of this site from the floor will be measured, such that caliper measurements at all following study assessments are performed at the same site.
- 9. Thigh gap measurement will be obtained.
 - Patient will be asked to stand with legs at a fixed distance apart. Measurement
 will be performed between sites of maximum bulge at Screening. Vertical
 distance of these sites from the floor will be measured, such that thigh gap
 measurements at all following study assessments are performed at the same sites.
- 10. Follow-up photographs will be taken.
 - Patients will be asked to stand with feet apart at a uniform distance.
 Anteroposterior and posteroanterior photos will be taken.

Week 12 Follow Up (~Day 190 to 232)

Visit expected to take 1 hour. The visit will take place 12 weeks after the last treatment.

- 1. Patient will be asked to complete Subject Self-Rating Scale, rated from 0 to 6.
- 2. Patient will be asked to complete Post-Treatment Satisfaction Questionnaire.
- 3. Concomitant meds and procedures will be confirmed and recorded.
- 4. Adverse events will be confirmed and recorded.
- 5. Patient weight will be obtained.
- 6. A relevant physical exam will be performed by the investigator.
- 7. Thigh circumference measurement will be obtained with anthropometric tape measure.
 - Thigh circumference will be measured at site of maximum bulge at Screening.
 Vertical distance of this site from the floor will be measured, such that thigh circumference measurements at all following study assessments are performed at the same site.
- 8. Caliper measurement of inner thigh skin-fold thickness will be obtained.
 - Caliper measurement will be performed at site of maximum bulge at Screening.
 Vertical distance of this site from the floor will be measured, such that caliper measurements at all following study assessments are performed at the same site.
- 9. Thigh gap measurement will be obtained.
 - Patient will be asked to stand with legs at a fixed distance apart. Measurement
 will be performed between sites of maximum bulge at Screening. Vertical

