- b) Patient satisfaction related to study treatment:
 - i. Improvement in patient satisfaction, as measured by
 Subject Self-Rating Scale, a 0 (extremely dissatisfied) to 6
 (extremely satisfied) scale
 - ii. Scores on additional post-treatment patient satisfaction questionnaire

B. Statistical methods

This is a small descriptive study, with the primary safety endpoint of the incidence rate of patients who experience:

- 1) Any adverse event (AE) ascertained by patient report, physician evaluation, or laboratory value
- 2) One or more serious adverse events (SAE) as defined by CTCAEv4
- 3) Adverse events leading to study drug discontinuation.

The safety analysis will be based on the safety population, which is defined as all patients who have received at least one dose of study medication and who have had at least one post-baseline safety evaluation.

Adverse events will be explored for trends.

The efficacy analysis will be based on the intent-to-treat (ITT) population. In the ITT population, patients will be counted in the treatment group upon informed consent and completion of Baseline measurements, regardless of receiving any dose of study medication.

In the case of a subject's early termination from study, missing values will be imputed using last observation carried forward (LOCF) method.

Baseline values will be those values measured on day of screening, which may be combined with Day 1.

Reduction in inner thigh fat, as measured by tape measure and calipers, will be presented as change in millimeters or centimeters, and presented descriptively. Percent accuracy by three independent blinded physicians in correctly identifying baseline photographs, when comparing before-and-after clinical photographs of the treatment area, will be reported. Patient satisfaction scores on Subject Self-Rating scale and post-treatment patient satisfaction questionnaire will be presented descriptively.

VII. Risks and Discomforts

A. Complications of treatment procedure/drug side effects and toxicities

Deoxycholic acid will be injected subcutaneously in the treatment area by the principal investigator [name], or by a member of the study team who is a UCSD Dermatology resident physician, under direction of [name].

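### Weight is recorded at every in-person visit but not used in Section VI, so the planned output shows raw thigh change without showing whether weight changed too

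*Combined protocol and SAP*

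**What the plan says.** Section II.A describes the design: "This prospective, open-label, single-arm, single-center clinical study". Section IV.D has both inner thighs treated, in one to four sessions.

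Section V.a lists weight ("Patient's weight will be obtained") at Screening and on Day 1. The same item appears at Treatments 2 to 4 and, in nearly the same words, at the Week 4 and Week 12 follow-ups.

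Section VI.A.2 makes efficacy a secondary endpoint, defined as less inner thigh fat and measured by circumference, skin-fold thickness, thigh gap and blinded photograph review. For the tape and caliper results, VI.B plans: "Reduction in inner thigh fat, as measured by tape measure and calipers, will be presented as change in millimeters or centimeters", presented descriptively. Weight appears nowhere in Section VI.

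Two inclusion criteria in III.A bear on weight. Criterion 5 reads "Stable body weight for previous 6 months (weight within 10 pounds of baseline", and criterion 9 reads "Subjects must be willing to avoid changes in diet or exercise, any weight loss program, and any weight loss supplements, during the study period".

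VI.B takes baseline from the day of screening, which may be the same day as Day 1. The visit headed "Screening/Baseline Visit (Visit 1, Day -14 to 1" lists weight but no thigh measurement. The first listed thigh value is on Day 1: "Thigh circumference measurement will be obtained with anthropometric tape measure".

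**The concern.** All three body measures can be expected to move with body weight. With no control subject and no untreated thigh, a weight loss can look like a treatment effect and a weight gain can hide one. The plan labels the raw before-after change as fat reduction and does not display the weight data that would let a reader judge the obvious rival explanation.

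Setting the two changes side by side also needs a common baseline. The stated rule points to a visit at which, on the listed procedures, only weight is taken.

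What is at stake is the interpretation of the secondary efficacy results. The primary safety endpoint is untouched. VI.B plans no test, interval or success criterion for efficacy, so no error rate or coverage is in question.

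**Working it through.** The plan gives no sample-size derivation, expected effect, variability or weight-change figure, so there is no figure of its own to reproduce. The check is of the text, followed by an illustration of scale.

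**1. Where weight and thigh values are listed (V.a).**

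| Visit | Weight | Thigh measures |
|---|---|---|
| Screening | item 4 | none listed |
| Day 1 | item 2 | items 5–7 |
| Treatments 2, 3, 4 | item 2 | items 6–8 |
| Week 4, Week 12 | item 5 | items 7–9 |

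Weight is listed at 7 of 7 in-person visits and thigh values at 6 of 7. Day 1 is the first listed visit with both.

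**2. How long weight has to change.** With one session on Day 1, the last visit is 12 weeks later, on Day 1 + 84 = 85: (85 − 1)/7 = 12.0 weeks. With four sessions, the latest fourth session is Day 148, and 148 + 84 = 232, which matches "Week 12 Follow Up (~Day 190 to 232". That gives (232 − 1)/7 = 33.0 weeks.

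**3. The baseline rule against the visit lists.** If Screening and Day 1 are combined, the rule works. If they are separate, up to about two weeks apart, the rule names a day with a weight but no listed thigh value. An analyst would then have to take the thigh baseline from Day 1, and might pair it with an older weight even though a Day 1 weight exists.

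**4. What the eligibility criteria cover.** Criterion 5 looks back six months and tolerates 10 pounds. Criterion 9 asks for willingness. Neither sets an on-study limit or says what the analysis does if weight changes.

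**5. Illustration of scale, circumference only.** Assumptions that are not in the documents: thigh circumference C of 50 to 65 cm, body weight W of 55 to 85 kg, and thigh cross-section proportional to body mass. Then C is proportional to √W, and the change per kg is C/(2W):
- low: 50/(2 × 85) = 0.294 cm/kg
- middle: 58/(2 × 70) = 0.414 cm/kg
- high: 65/(2 × 55) = 0.591 cm/kg

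If the thigh takes only half that share, the range is 0.147 to 0.295 cm/kg. Overall this is roughly 0.15 to 0.6 cm per kg of mean weight change, in either direction. No figure is offered for skin-fold or thigh gap.

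**6. Why the display should use measured pairs.** The ITT set in VI.B counts subjects from consent and completed baseline even if never dosed, and values missing after early termination are carried forward. A subject with baseline only would then enter as zero thigh change and zero weight change. If, say, 2 of 15 were such subjects, the mean change would be 13/15 = 0.867 of the mean in those actually measured, whatever happened to weight.

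**7. Would a regression to zero weight change be better?** Not reliably at n = 15. In a simulation with assumed inputs (residual SD 1 cm, one thigh value per subject):
- If weight is irrelevant (slope 0), the adjusted interval is wider than the crude one by a factor of 1.045 at zero mean weight change, 1.18 at mean 1 kg/SD 2 kg, 1.51 at mean 2 kg/SD 2 kg, and 2.43 at mean 2 kg/SD 1 kg.
- In the last case all 15 weight changes lie on one side of zero with probability Φ(2)^15 ≈ 0.71, so the estimate would usually be an extrapolation.
- At slope 0.207 cm/kg and mean 1 kg/SD 1 kg, root mean squared error is 0.39 adjusted against 0.34 crude. At mean 1 kg/SD 2 kg it is 0.30 against 0.35.

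**The case against.** The strongest reply is that nothing is lost. Weight and thigh values are recorded for each subject on Day 1 and at every later in-person visit, so they can be set side by side at any time. That stands. A reader might infer that thigh change in this study cannot be told apart from weight change at all. The documents do not support that, because the gap is in the planned output and not in the data.

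Criteria 5 and 9 are real design controls on this confounder, and nothing in the documents shows that mean weight will drift. That also stands. They reduce the risk without making it visible, and whether they worked can be seen only if weight change is reported.

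The study calls itself small and descriptive, and these endpoints are secondary. This limits the severity but does not remove the point, because a descriptive study informs only through what it displays.

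On baseline, the protocol does state a rule, and V.a places every measurement at the fullest point of the thigh as found at Screening, so some thigh assessment then is implied. The Schedule of Events that V.c refers to is not in the supplied text and may list more. The narrower point stands: on the visit lists as written, the rule and the measurements do not match when the visits are separate.

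A reader might also infer that a weight-adjusted estimate should be required. Step 7 shows that it is a trade-off. It would also have to settle how to use two thighs per subject, and how to handle one to four sessions, which link treatment received to length of follow-up.

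**Conclusion.** The point holds as a low-severity reporting and interpretation improvement. Weight is collected at all seven in-person visits and is unused in Section VI. The planned output presents raw change over 12 to 33 weeks as fat reduction, without showing whether weight changed. The screening-day baseline does not fit the listed thigh measurements when Screening and Day 1 are separate.

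The size of any effect is unknown from the documents. The 0.15 to 0.6 cm per kg figure rests wholly on the assumed thigh sizes, body weights and scaling. It shows scale for circumference and is not an estimate of bias in this trial.

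A reader might infer that the efficacy results are biased or that the safety conclusion is weakened. Neither follows: no weight drift is shown, and the primary endpoint does not depend on the thigh measures.

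**What to change.** In VI.B:

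1. Define baseline for weight, circumference, skin-fold and thigh gap as the Day 1 pre-treatment values, replacing the screening-day rule for these measures.
2. At each later visit, report change in weight beside change in circumference, skin-fold and thigh gap, using subjects with both weight and the thigh measure actually observed at that visit, and give the number of subjects.
3. Add a per-subject plot of thigh change against weight change.
4. State that a thigh change will not be described as fat reduction from treatment without giving the accompanying weight change, and that this display does not replace a control arm.

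A regression estimate at zero weight change is at most an optional exploratory analysis.

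The cost is one table column and a plot, on data already collected. The efficacy result may look less favourable if weight fell. Unblinded tape and caliper measurement and the other limits of a single-arm study remain.

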APPENDIX I. Subject Self-Rating Scale

How satisfied are you with the current appearance of your upper inner thighs?

Extremely satisfied (6)	
Somewhat satisfied (5)	
Slightly satisfied (4)	
Neither satisfied nor dissatisfied (3)	
Slightly dissatisfied (2)	
Somewhat dissatisfied (1)	
Extremely dissatisfied (0)	

APPENDIX II. Post-Treatment Satisfaction Questionnaire

1. Were you satisfied with the Kybella treatments you received for reduction of inner thigh fat?

Yes/No

2. Have you noticed a reduction in inner thigh fat, compared to prior to treatments?

No improvement

0-25% improvement

25-50% improvement

50-75% improvement

75-100% improvement

3. Would you recommend Kybella treatments to a friend interested in reducing inner thigh fat?

Yes/No

4. Considering the side effects and disadvantages, would you undergo Kybella treatment for reduction of inner thigh fat again?

Yes/ No

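### Item 2 of the post-treatment questionnaire has overlapping answer bands and no option for worsening, so an unchanged subject can be counted as improved and a worse subject is hidden among the unchanged

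*Combined protocol and SAP*

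**What the plan says.** Appendix II, item 2, asks "Have you noticed a reduction in inner thigh fat, compared to prior to treatments". The five possible answers are "No improvement", "0-25% improvement", "25-50% improvement", "50-75% improvement" and "75-100% improvement". Items 1, 3 and 4 of the same form are Yes/No.

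The form is completed at the Week 4 and Week 12 follow-up visits (Section V). It supports secondary endpoint b(ii) in Section VI.A: "Scores on additional post-treatment patient satisfaction questionnaire". Section VI.B says only that the "post-treatment patient satisfaction questionnaire will be presented descriptively". Neither section says how item 2 is scored or which summary is reported.

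The study is open-label and single-arm (Section II.A), with 15 subjects (Section IV.A).

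**The concern.** There are three drafting faults in one item.

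- **Shared boundaries.** Each improvement band begins where the previous option ends, so some answers fit two boxes. The overlap at zero matters most, because it lies on the line between improved and not improved.
- **No worse category.** A subject who thinks the inner thigh has more fat than before has only the null answer to tick. The data cannot then separate no change from worsening.
- **One-directional stem.** The question asks about reduction and does not invite the opposite answer.

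This is the only question that asks subjects directly how much their fat changed. With no control arm, no comparison can show how far the answer format shaped the replies. What is at stake is how a descriptive table can be read. The share improved may include unchanged subjects, and the null row may include worse ones.

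**Working it through.** The plan states no figure for this item, so there is none to reproduce. Three checks follow.

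**1. Which values fit more than one option?** Inputs: the five options in Appendix II, read as 0, 0 to 25, 25 to 50, 50 to 75 and 75 to 100 with both ends included, since the form excludes neither. Going through the whole percentages from 0 to 100, four fit two options:

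| Value | Options that fit |
|---|---|
| 0 | no improvement; 0 to 25 |
| 25 | 0 to 25; 25 to 50 |
| 50 | 25 to 50; 50 to 75 |
| 75 | 50 to 75; 75 to 100 |

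At 25, 50 and 75 the subject may choose the higher or the lower band, and nothing in the form favours either. Those overlaps have no fixed direction, and both choices count as improved. At 0 the only possible error is upward, from not improved to improved.

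**2. What can the overlap at 0 do to the share improved?** Input: n = 15 (Section IV.A), all assumed to answer. If u unchanged subjects tick the lowest band, the share improved rises by u/15:

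- u = 1: 1/15 = 6.7 percentage points
- u = 2: 2/15 = 13.3 points
- u = 3: 3/15 = 20.0 points

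The documents give no basis for choosing u, so this is a cost per subject and not an estimate of bias.

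**3. What does the missing worse option do?** A worse subject is recorded in the null row.

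*Share improved.* Worse subjects are outside the numerator with or without a worse option. The share does not change.

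*Mean category score.* Suppose the null answer were coded 0, the bands 1 to 4, and a worse option -1 (assumed coding; the plan has none). Recording k worse subjects as 0 instead of -1 raises the mean by k/15: 0.067 for k = 1, 0.133 for k = 2 and 0.200 for k = 3.

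*Mean percentage change.* Suppose perceived change is Normal with mean μ and standard deviation σ (both assumed). Recording every negative value as 0 gives a mean of μΦ(μ/σ) + σφ(μ/σ). For μ = 10 and σ = 25, this is 10 × 0.655 + 25 × 0.368 = 15.8, a shift of 5.8 points. The share above zero is Φ(0.4) = 0.655 before and after. Across a range of assumptions:

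| Assumed μ | Shift at σ = 15 | Shift at σ = 25 |
|---|---|---|
| 0 | 6.0 | 10.0 |
| 10 | 2.3 | 5.8 |
| 25 | 0.3 | 2.1 |
| 40 | 0.0 | 0.6 |

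The shift runs from nothing to 10 points depending on two values that the documents do not give, and it arises only if a mean is reported. The table shows the direction and the dependence. It does not measure bias in this trial.

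**The case against.** The strongest case on the other side is that little depends on this item. It is one of four questions in one of two satisfaction measures, untested, in a study that the plan itself calls small and descriptive. Bad outcomes can be seen elsewhere. Items 1, 3 and 4 accept a negative answer. The 0 to 6 Subject Self-Rating Scale (Appendix I) has a dissatisfied range. Circumference, caliper thickness and thigh gap can move either way. Swelling and hardness (Section VII.A) are collected as adverse events, and nothing in the documents indicates that subjects would report them as added fat at 4 or 12 weeks. All of this stands, and it keeps the severity low.

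It does not repair item 2. A No on satisfaction, recommendation or repeat treatment does not mean worse. The self-rating scale asks about satisfaction with current appearance, not change. Entry requires a score of 0 to 2 (Section III.A, inclusion criterion 3), so that scale has little room to fall, and none for a subject entering at 0. The physical measurements are not the subject's own report of change.

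Three stronger readings are tempting, and the documents do not support them:

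- *The item can only record improvement.* It cannot, because a null answer is offered. Worsening is merged with no change and is not turned into benefit.
- *The satisfaction endpoint is biased upward by a known number of points.* Any such number needs an assumed spread, an assumed true change and a mean score that the plan does not define.
- *With no true effect, about half the subjects would appear improved because of this form.* That fraction comes from assuming perceived change symmetric around zero. Exclusive bands with a worse option would give the same fraction.

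**Conclusion.** The point holds as a drafting defect of low severity. Three things can be read directly from Appendix II: adjacent bands share 25, 50 and 75; zero change fits both the null answer and the lowest improvement band; and worsening has no box of its own. The stem adds a one-directional prompt whose effect cannot be sized.

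Only the ambiguity at zero and the stem could plausibly raise the share improved. For the ambiguity, the cost is 6.7 percentage points per misplaced subject, assuming all 15 answer; the number misplaced is unknown. The missing worse option loses information in every summary, but it inflates only a mean-type score. The conclusion needs no assumption about the treatment effect and claims no overall bias for the satisfaction endpoint.

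**What to change.** Before the form is first used:

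1. Replace the item 2 options with: Worse; No change; more than 0 to 25% improvement; more than 25 to 50%; more than 50 to 75%; more than 75 to 100%.
2. Reword the stem neutrally, for example: *How has your inner thigh fat changed compared with before treatment?*
3. State in Section VI.B that item 2 is reported as the number of subjects in each category at Week 4 and at Week 12, with no mean score.

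The cost is one edit to a short form and one sentence in the analysis section, with the approval that any change to the form needs. Sample size, visits and treatment are unaffected. If forms have already been completed, report the counts in the five existing categories and state that the null row may include worse subjects and the lowest band may include unchanged ones.
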